7.2.3 Body Temperature

MDMA administered in a controlled setting produces only a slight increase in body temperature [124]. Ambient temperature does not enhance or attenuate this slight elevation in humans.

If temperature rises more than 1° C, attempts will be made to lower it by removing blankets and layers of clothing, decreasing the ambient temperature, and, if necessary, directing a fan toward the subject. If at any time the temperature rises more than 1.5° C above baseline despite these efforts, the PI will be present at all times and will determine the need for further evaluation and treatment.

7.2.4 Reproductive and Developmental Risks

Risks posed by MDMA to pregnant women are not known. One of two studies of Ecstasy users suggests that use of Ecstasy and other drugs during pregnancy may be associated with some abnormalities at birth while the other failed to find this association [164, 165], and a third reported some developmental delays in mothers reporting use of ecstasy and other drugs during pregnancy [166]. These studies are discussed in the IB.

Pregnant and lactating women will be excluded from participation in the study. Women who are able to become pregnant must have a negative pregnancy screen before undergoing each experimental session and must agree to use birth control for the treatment portion of the study.

7.2.5 Potential Neurotoxicity Associated with Ecstasy Use

Some researchers believe that MDMA is neurotoxic in humans even at doses used in clinical trials [167]. However, they are basing their case on studies that employed inappropriately high doses of MDMA utilized in animal studies and on human studies comparing the effects of repeated use of Ecstasy, often along with other drugs. Meanwhile, another recently published meta-analysis has taken careful steps to overcome methodological limitations in previous work and found only modest evidence of neurotoxicity [168]. We have carefully considered the risks of such neurotoxicity and conclude that they are minimal in the proposed study. This conclusion is supported by empirical and toxicokinetic evidence and is consistent with the lack of toxicity reported in previous clinical MDMA studies. More information on the potential neurotoxicity of MDMA can be found in the IB.

7.2.6 Risk Mitigation

Careful review of medical screening data will be utilized to exclude potential subjects with pre-existing exclusionary medical conditions from the study. Study procedures have been developed to mitigate the risks of receiving MDMA described in detail in the IB. Ambient temperature will be kept at a comfortable level during Experimental sessions. Subjects will not be allowed to drink more than 3L of fluids over the course of the experimental session and fluid intake will be spread out appropriately during the session. Fluids administered will include electrolytes. If a subject exhibits any signs of toxicity or clinically significant dilutional hyponatremia despite these precautions after an experimental session, subjects will be excluded from receiving future experimental sessions, unless approved by the PI, Data Safety Monitor, and the Medical Monitor.

7.3 Abuse Liability

Findings in humans and animals suggests that MDMA possesses moderate abuse potential that is higher than that reported for “classic hallucinogens,” like psilocybin, but lower than that reported for psychostimulants, such as cocaine or methamphetamine. More information on abuse liability is provided in the IB.

To ensure MDMA-assisted therapy does not cause autistic adults to develop symptoms of drug abuse after the treatment period of the study, drug use is monitored during the follow-up period. Based on long-term follow-up data from two sponsor-supported studies (N=32), only one subject took Ecstasy after completing the study and failed to reproduce the experience from the study and a number of subjects volunteered that they would never seek out Ecstasy outside a legal, controlled, therapeutic setting. In addition, negative results from MDMA-specific drug testing data obtained from the Swiss study MP-2 (N=12) supports that none of these subjects took Ecstasy outside of the study during a 12-month follow-up period.

Diversion is not an issue in this protocol because MDMA will only be administered in a controlled environment under the supervision of the PI and no take-home doses will be permitted. MDMA will be handled following all regulations pertaining to the handling and dispensing of controlled substances within research studies.

8.0 Adverse Events

8.1 Adverse Events

An adverse event (AE) is defined as any untoward or unfavorable medical occurrence in a clinical research study subject, including any abnormal sign (e.g. abnormal physical exam or laboratory finding), symptom, or disease, temporally associated with the subject's involvement in the research, whether or not considered related to participation in the research. This definition includes concurrent illnesses or injuries and exacerbation of pre-existing conditions.

An *unexpected adverse event* is one that is not listed in the current IB or an event that is by nature more specific or more severe than a listed event.

All AEs will be monitored by the therapists until resolution or, if the AE becomes chronic, a cause can be identified. If an AE is unresolved at the conclusion of the protocol, a clinical assessment will be made by the CI and/or Medical Monitor as to whether continued follow-up of the AE is warranted.

The severity of events reported on the "Adverse Events" CRF will be determined by the PI as:

- Mild: No limitation in normal daily activity
- Moderate: Some limitation in normal daily activity
- Severe: Unable to perform normal daily activity

The relationship of the study treatment to an AE will be determined by the PI based on the following definitions:

1. "Not Related": The AE is not related if exposure to the investigational product has not occurred, or the occurrence of the AE is not reasonably related in time, or the AE is considered unlikely to be related to use of the investigational product, i.e. there are no facts (evidence) or arguments to suggest a causal relationship, or the AE is more likely related to the subject's pre-existing condition.
2. "Possibly Related": The administration of the investigational product and AE are considered reasonably related in time and the AE could be explained by causes other than exposure to the investigational product.
3. "Probably Related": Exposure to the investigational product and AE are reasonably related in time and the investigational product is more likely than other causes to be responsible for the AE, or is the most likely cause of the AE.

8.2 Spontaneously Reported Reactions

Commonly expected spontaneously reported reactions to MDMA are collected on a separate CRF page and will be categorized as mild, moderate, or severe. Common, expected reactions are defined as those most frequently reported in the literature and include: Anxiety, Diarrhea, Difficulty Concentrating, Dizziness, Drowsiness, Dry Mouth, Fatigue, Headache, Heavy Legs, Impaired Gait/Balance, Impaired Judgment, Increased Irritability, Insomnia, Jaw Clenching or Tight Jaw, Lack of Appetite, Low Mood, Muscle Tension, Nausea, Need More Sleep, Nystagmus, Parasthesias, Perspiration, Restlessness, Rumination (increased private worries), Sensitivity to Cold, Thirst, and Weakness.

Spontaneously reported reactions will be collected during the experimental session and the seven days of telephone contact following the integrative session that occurs on the day after each experimental session. Each reported reaction will be followed during follow-up phone calls or visits until resolution. Reactions that persist beyond the seven days after each experimental session will be recorded as AEs on the AE CRF page.

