8.5 Adverse Event Collection

The PI will be responsible for reviewing and confirming all AEs and SAEs collected during the study. The co-therapist or PI will collect AEs during study visits after enrollment.

All SAEs will be collected for the duration of the protocol. All SAEs which occur during the course of the trial, whether considered to be associated with the study drug or not, have to be reported within 24 hours of the CI's awareness of their occurrence. All SAE reports should be faxed to the sponsor. A fax number will be provided to the site in separate site-specific instruction for SAE reporting. In addition to the fax, the PI, or designee should call the Clinical Research Associate (CRA) during normal working hours and verbally inform the CRA of the SAE. During off business hours or if medical advice is needed immediately, the sponsor Medical Monitor will be called. SAE reporting instructions with all contact numbers will be provided to the site prior to study start.

The following symptoms will be assessed at baseline and exacerbations during the study will be tracked and categorized as mild, moderate, or severe on a separate Symptoms CRF log page: Persistent feelings of alienation, Rigidity, Tremor, Dystonic Symptoms, Akathisia, Increased Motor Activity, Decreased Motor Activity, Sensory Hyperarousal, Excitement/Agitation.

AEs to be collected during the study are:

- Serious Adverse Events (SAEs) will be collected from enrollment through termination.
- All AEs and spontaneously reported reactions will be collected on the day of and seven days after each experimental session or until they resolve.

- AEs requiring medical attention, including a doctor visit or treatment with prescription medication, will be collected from the first experimental session through the final integrative session after the second experimental session.
- AEs related to planned treatments or physician visits for baseline conditions collected in the Medical History will not be collected unless there is an exacerbation of the condition.
- Any AE leading to withdrawal will be collected throughout the study.
- All AEs related to changes in psychiatric status will be collected throughout the study.
- Any exacerbations of Symptoms recorded at Medical History will be collected throughout the study.

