Descriptive statistics will be computed for vital signs and subjective distress during each experimental or open-label session. The sponsor will compare pre-drug and post-drug peak blood pressure, heart rate, and body temperature during and after all experimental sessions by condition and MDMA dose. Analyses will compare peak vital signs between MDMA and placebo subjects, and a separate analysis will consider the effects of dose (0, 75, 100 or 125 mg MDMA) upon vital signs.

Frequency tables will be produced on prevalence of spontaneously reported reactions and AEs. Number and severity of spontaneously reported reactions will be compared in MDMA and placebo subjects using a one-way analysis of variance (ANOVA). The effects of MDMA dose upon number and severity of spontaneously reported reactions will also be assessed. Presence and degree of exacerbated symptoms across MDMA and placebo participant will also be examined.

Perceptions of study participation will be examined at baseline, 6-month follow-up, and end of Stage 2 using the Feedback Questionnaire and a qualitative interview. The results of this qualitative analysis will inform the sponsor of expectancies and perceptions about study procedures for future protocol development. Similarly, belief of condition assignments collected during Stage 1 will be used to assess the effectiveness of the double-blind in preparation for future studies. Results from the Feedback Questionnaire and safety data will be utilized to find the appropriate active MDMA dose for future studies.

To facilitate the planning of future studies, a preliminary estimate of effect size may be performed after all the subjects have completed the outcome assessments, one month after the second experimental session, but not all subjects have completed the six-month follow-up evaluation. This preliminary estimate will consist of safety and outcome measures. Results of the preliminary estimate will have no effect on study conduct.

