3.3 Safety Objectives

The safety objectives of the study are to monitor and assure safety of subjects during and after the experimental sessions by assessing physiological effects, psychological distress, adverse events, spontaneously reported reactions and suicidality.

- Vital signs (BP, HR, BT) will be measured at baseline and every hour during experimental sessions until they return to baseline.
- Participant distress will be measured by the Subjective Units of Distress (SUD) scale at baseline and every hour during experimental sessions until return to baseline.
- Risk of suicide will be measured by the Columbia Suicide Severity Rating Scale (C-SSRS) during all in person visits, as well as twice during each experimental session at two hours after drug administration and the end of the experimental session, and on Day 2 and Day 7 after each experimental session.
- SAEs and AEs will be assessed throughout the study and spontaneously reported reactions, defined as expected AEs, will be assessed during each experimental session and for seven days after each experimental session, or until resolution.
- In addition to spontaneously reported reactions, symptoms specific to the study population will be collected at baseline and tracked throughout the study

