7.2 Safety Measures

- Columbia Suicide Severity Rating Scale (C-SSRS)
- Subjective Units of Distress (SUD)
- General Well-being (GWB)
- Symptoms Specific to Population
- Vital signs (systolic blood pressure (SBP), diastolic blood pressure (DBP), heart rate (HR), body temperature (BT))
- Adverse Events (AE), including Spontaneously Reported Reactions (SRR)

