8.10.4 Safety Analyses

The primary measure of safety will be the reporting of adverse events. The Adverse events considered are Treatment Emergent Adverse Events (TEAE) defined as those AE's that occurred after dosing and those existing AEs that worsened during the study. Verbatim terms on case report forms will be mapped to preferred terms and system organ classes using the MedDRA dictionary. For incidence reporting if a subject has more than one adverse event mapped to the same preferred term, that adverse event will be reported only once using the highest severity and closest relationship to study drug. Subject incidence of adverse events will be displayed by Stage I treatment group and by system organ class. Adverse events will also be summarized by severity and relationship to study drug. Subject incidence of serious adverse events by Stage I treatment group will also be displayed. In addition to the listing of all adverse events, a listing of serious adverse events and a listing of adverse events leading to discontinuation of study drug will be included.

Summary tables of frequency listings of expected adverse events (Spontaneously Reported Reactions) mapped to preferred terms will be displayed during and after each experimental session by Stage I treatment group.

Columbia Suicide Severity Rating Scale (C-SSRS)

Suicidal ideation and behavior will be summarized according to suggestions made in the Columbia-Suicide Severity Rating Scale Scoring and Data Analysis Guide [3]. A positive response for suicidal ideation is counted when a subject answers "yes" to any one of the five suicidal ideation questions (Categories 1-5) on the C-SSRS, i.e. a score > 0 for suicidal ideation score. Serious suicidal ideation is a suicidal ideation score of 4 or 5. A positive response for suicidal behavior occurs when a subject answers "yes" to any one of the five suicidal behavior questions (Categories 6-10) on the C-SSRS, i.e. a score > 0 for suicidal behavior score. The number and percent of positive responses of Positive Ideation, Serious Ideation, and Positive Behavior will be tabulated by Stage I treatment group and time period. Compare lifetime serious suicidal ideation and positive behavior frequencies to cumulative frequencies anytime during the study until end of stage 1 and stage 2.

Subjective Units of Distress (SUD)

Descriptive statistics for SUD scores will be calculated by Stage I treatment group and time period with counts and percentages.

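### The plan leaves open whether listed reactions count as adverse events, and the SAP drops the reaction severity comparison that Protocol 12.0 plans

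*Protocol*

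**What the plan says.** **Collection.** Protocol 8.2 lists 27 expected reactions, among them anxiety, low mood, increased irritability, insomnia and rumination. It says: "Commonly expected spontaneously reported reactions to MDMA are collected on a separate CRF page and will be categorized as mild, moderate, or severe". The only route it gives from that page to the AE page is persistence: "Reactions that persist beyond the seven days after each experimental session will be recorded as AEs on the AE CRF page".

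**Classification.** SAP 3.3, in wording shared with Protocol 3.3, treats them as AEs: "spontaneously reported reactions, defined as expected AEs, will be assessed during each experimental session and for seven days after each experimental session". SAP 7.2 names one safety measure covering both: "Adverse Events (AE), including Spontaneously Reported Reactions (SRR".

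**Analysis in the SAP.** SAP 8.10.4 makes AE reporting the primary safety measure. It defines treatment-emergent AEs (TEAEs) as those arising after dosing or worsening during the study, and does not mention the reaction page. It then says: "Adverse events will also be summarized by severity and relationship to study drug". Reactions get a separate output: "Summary tables of frequency listings of expected adverse events (Spontaneously Reported Reactions) mapped to preferred terms will be displayed", by session and Stage 1 group. Severity is not mentioned there. SAP 8.0 sends data that the plan does not analyse to listings only.

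**Analysis in the protocol.** Protocol 12.0 plans more: "Number and severity of spontaneously reported reactions will be compared in MDMA and placebo subjects" by one-way ANOVA, with dose effects on both quantities also assessed.

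**A second collection rule.** Protocol 8.5 states: "All AEs related to changes in psychiatric status will be collected throughout the study".

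**The concern.** Protocol 12.0 describes the trial as mainly a safety study, so the contents of its primary safety measure should not be open to choice. Two programmers working from the same database could produce different TEAE incidence tables. One would read SAP 7.2 and count the reactions; the other would read Protocol 8.2 and use the AE page only. If that choice is made after results by arm are known, the headline AE rate becomes a data-dependent decision.

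The second loss is in the reaction table. The grade is collected and the protocol intends to compare it, but the SAP's table for these events shows frequency only. In a trial of an anxiety treatment, a reader judging tolerability needs to know whether post-session anxiety or low mood was mild or severe.

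Protocol 8.2 and 8.5 also overlap without a rule between them. Worsened anxiety in the first week is a listed reaction under 8.2 and could be a change in psychiatric status under 8.5. The text does not say which page it belongs on.

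**Working it through.** The documents state no figure to reproduce. The check sets the rules side by side on a test case, then illustrates how common such cases may be.

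**Step 1: a test case.** Take a subject with severe fatigue (a listed reaction) that starts the day after a session and resolves on day 4. It is untreated, not serious, and does not lead to withdrawal. It ends inside the window, so 8.2 keeps it on the reaction page, and none of the serious, medically attended, withdrawal or psychiatric-status routes in 8.5 clearly applies.

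| SAP output | AE tables from the AE page only | Reactions counted as AEs (SAP 7.2) |
|---|---|---|
| TEAE incidence | absent | present |
| AE severity table | absent | present |
| AE relationship table | absent | required; whether a relationship grade is recorded cannot be seen |
| Reaction table | present, without grade | present, without grade |
| Listings | grade appears | grade appears |

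TEAE membership changes with the reading. The reaction table lacks the grade on both readings, so the departure from Protocol 12.0 in that table does not depend on how membership is settled.

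**Step 2: the trigger.** Protocol 8.2 turns on persistence past the seven-day window, not on duration. A six-day reaction that starts on day 3 runs past the window and reaches the AE page; one that starts on the session day does not.

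**Step 3: illustration of frequency.** Inputs: Protocol 7.2 gives 40% to 80% of subjects, in both conditions of the sponsor's earlier PTSD study (N=23), for anxiety, headache, fatigue, insomnia and lack of appetite. Allocation is 8 MDMA to 4 placebo. Assumption: those rates carry over to this population.

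- Expected subjects per term, n × p: MDMA 8 × 0.40 = 3.2 to 8 × 0.80 = 6.4; placebo 4 × 0.40 = 1.6 to 4 × 0.80 = 3.2.
- Chance that at least one subject reports a given term, 1 − (1 − p)^n: MDMA 0.983 to above 0.999; placebo 0.870 to 0.998.
- Share of subjects with at least one of the five terms: 40% to 80% if the terms overlap completely; if independent, 1 − 0.6^5 = 92% to 1 − 0.2^5 = above 99.9%.

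**Step 4: severe reactions.** The documents give no rate. At an assumed 5% to 20% of subjects, 8 × 0.05 = 0.4 to 8 × 0.20 = 1.6 MDMA subjects would have one, and the chance of at least one is 0.34 to 0.83.

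Steps 3 and 4 show that the unresolved cases are likely to occur. They do not give the difference between readings, which needs the share of reactions resolving within the window. The documents do not report that share.

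**The case against.** The strongest reply is that the layout is coherent. Protocol 8.2 says which form is used, not that reactions are not AEs. SAP 8.10.4 itself calls them expected AEs and gives them a table by session and arm, so one clarifying sentence would settle membership. This largely stands, and it limits the membership issue to a clarification. It does not restore the severity comparison.

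Several stronger readings are tempting and are not supported:

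- **That short severe reactions enter no severity table at all.** This is true only if AE tables use the AE page alone. On the SAP 7.2 reading they fall under the AE severity summary.
- **That important reactions are lost.** Protocol 8.5 separately collects serious events, events needing a doctor visit or prescription treatment, events leading to withdrawal, and psychiatric-status events. Nothing in 8.2 exempts listed reactions from these rules, so severe anxiety treated with a prescribed rescue drug appears collectable as an AE whatever its duration.
- **That the relationship table cannot be filled.** Protocol 8.1 has the investigator assign relationship to any AE, and the CRF is not among the documents. Silence in 8.2 does not show that the grade is missing.
- **That acute distress is otherwise unmeasured.** The SUD scale is taken about hourly in sessions and tabulated by group and time. The BDI-II and STAI are taken one day and two weeks after each session. These cover distress, mood and anxiety, but do not grade most of the other listed reactions.

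It is also fair to object to merging both pages into one incidence table. With 8 and 4 subjects, near-universal minor reactions could hide other events. The 8.1 severity definitions are written for the AE page, and 8.2 gives no anchors for its grades. Merging is therefore a matter of preference, not a necessary correction.

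**Conclusion.** The concern holds in a limited form. First, SAP 8.10.4 does not fix whether events confined to the reaction page are TEAEs, so the primary safety measure depends on the reading. Second, its reaction table omits severity, although Protocol 8.2 collects the grade and Protocol 12.0 plans to compare it. On the AE-page reading, the grades of reactions that end within the window and are not otherwise collected under 8.5 appear only in listings.

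The size of the effect on AE incidence is unknown. A reader might take the 92% to above 99.9% range as the gap between readings. It is not: it assumes independence, borrows rates from a PTSD population, applies to both conditions, and says nothing about duration or severity. The textual conclusion rests on none of those figures. The change should be made because it is cheap and the trial is mainly about safety, but nothing here suggests that safety data go uncollected.

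**What to change.** In SAP 8.10.4:

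1. Tabulate reactions by preferred term and maximum severity, by Stage 1 arm, session and dose, and restore the number-and-severity comparison from Protocol 12.0. Stage 1 gives 4 planned sessions at 75 mg, 8 at 100 mg, 4 at 125 mg and 8 on placebo, so the table will be more informative than any test.
2. State whether reaction-page events enter the TEAE incidence and severity tables, and label every AE table, including the relationship table, with the CRF page or pages that supply it.

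Settle this before unblinding. Because blinds are broken subject by subject at six months (Protocol 5.2.7), and Protocol 12.0 allows an earlier preliminary look that includes safety measures, the decision should precede whichever comes first.

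In the protocol, reconcile 8.2 with the psychiatric-status rule in 8.5, so that the recording page for first-week changes in anxiety or mood is stated.

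The cost is SAP wording, table programming and a clarifying protocol sentence. The severity grades are already collected, so item 1 needs no new data.
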